9.2 Power Analysis

We estimate that 191 providers caring for 1468 eligible patients will provide 80% power to observe an 11 percentage-point difference in prescribing rates between each intervention arm and control, assuming a control arm prescribing rate of 30%, an ICC of 0.07, an average of 7 patients per provider, and a type I error rate of 5%.

10. Monitoring and Quality Assurance

10.1 Adverse Events and Reporting

Oversight of the pilot will be the responsibility of the pilot PI: [name], MPH. [name] and study investigators will meet on a regular basis throughout the study period and will be in direct contact with the peer PCPs to obtain ongoing feedback. In addition, the protocol will undergo Institutional Review Board (IRB) evaluation.

De-identified study data will be accessible at all times for the BWH pilot PI and coinvestigators to review, if applicable. The study team will also ensure that all protocol deviations for the pilot study are reported to the NIH and the IRB according to the applicable regulatory requirements. Compliance of regulatory documents and study data accuracy and completeness will be maintained through an internal study team quality assurance process.

Definition:

Adverse Event (AE): Any untoward or unfavorable medical occurrence in a human study participant, including any abnormal sign (e.g., abnormal physical exam or laboratory finding), symptom, or disease, temporally associated with the participants' involvement in the research, whether or not considered related to participation in the research.

Adverse Events will be classified using the following rating scales:

- Severity: Mild, Moderate or Severe
 - Mild: Awareness of signs or symptoms but are easily tolerated
 - Moderate: Events introduce a low level of inconvenience or concern but may interfere with daily activities but are usually improved by simple therapeutic measures.
 - Severe: Events interrupt the participants' normal daily activities and generally require systemic drug therapy
- Expectedness: Unexpected or Expected
 - Unexpected: nature or severity of the event is not consistent with the condition under study.
 - Expected: event is known to be associated with the intervention or condition under study

Serious Adverse Event (SAE): Any adverse event that:

- Results in death
- Is life threatening, or places the participant at immediate risk of death from the event as it occurred
- Requires or prolongs hospitalization

- Causes persistent or significant disability or incapacity
- Results in congenital anomalies or birth defects
- Is another condition which investigators judge to represent significant hazards

Given the minimal risk nature of the study, in which the intervention involves enhanced education and guideline concordant care for patients with at MGB, the PI does not expect any SAEs or AEs related to the information delivered in this trial. Patients' own primary care physicians will have ultimate decision-making authority for prescribing choices, as they would in routine clinical practice, and we expect any adverse events related to diabetes medication prescribing, such as hypoglycemia, to be the same as those experienced in routine clinical care.

Reporting:

As previously described, no additional SAEs or AEs are expected as part of this study. Any adverse event from medication prescribing will be handled in the course of regular clinical care, as is done currently, and through established safety reporting and review systems within MGH. In his role as the Director or Population Health and Quality in the Division of General Internal Medicine at MGH, [name] routinely reviews the safety reporting within MGH primary care and can be alerted to any reports that may relate to the study intervention.

Any reports of deaths will be submitted to the NIA Program Officer and to the NIA-appointed Standing Roybal DSMB Chair within 24 hours of the study team's knowledge. Any unexpected SAEs will be reported to the NIA PO and DSMB Chair within 48 hours of the study's knowledge of the SAE. All other reported SAEs received by the study team will be reported to the NIA Program Officer and to the DSMB quarterly, unless otherwise requested by the DSMB. AEs will be reported per IRB policies. They will also be reported to the NIA and DSMB at a frequency requested by NIA and/or by the DSMB (annually, at a minimum).

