All providers will receive the second personal outreach 6 months after the start of the intervention. The outreach will consist of an email notifying them that the study is ending and inviting them to participate in a brief survey. The fact sheet for survey participation will be attached to the email. The survey will be accessed through a unique link to a secure REDCap survey embedded into the email. REDCap is a secure, HIPAA-compliant web-based platform hosted on Mass General Brigham servers. Providers who click on the link to the survey will be met with a landing page that displays the fact sheet describing the study. They will then be able to click a button to indicate that they agree to participate. Providers who select that they agree will then proceed to the rest of the survey. All providers will be allows to respond. Participants will be offered remuneration in the form of a \$25.00 Amazon gift card for completing the survey. An email will be sent to the physician upon completion of the survey containing the claim code they will use to access their gift card. In addition, an electronic copy of the prescribing chart given to intervention arms, providers will also receive a list of the patients who remain eligible for one of these medications but who have not had a visit during the study intervention period. Providers will then have

the option to ask their administrative staff to schedule visits with these patients, consider prescribing asynchronously, or otherwise generate a plan of care. The survey to intervention providers will capture opinions on the interventions, mechanisms behind diffusion of responsibility in prescribing these medications, and thoughts about potential helpful interventions moving forward. Providers in the control arm will only be asked the questions about mechanisms behind diffusion of responsibility in prescribing these medications and thoughts about potential helpful interventions moving forward. All providers who have not completed the survey within 2-3 weeks of receiving the email invitation will receive a follow-up email asking them again to participate in the survey.

Providers randomized to arm 3, usual care, will not receive any outreach outside of the end of study notification and survey.

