After study completion, we will conduct an exploratory chart review of the visit notes from a random sample of patients in all three arms. Within each study arm, we will randomly sample visit notes from charts of 20 patients who were prescribed an SGLT-2i or a GLP1RA during the target visit (primary outcome occurred) and 20 patients who did not receive a prescription (primary outcome did not occur) to qualitatively explore the nature of the conversations that were documented at the visit. This will also include reviewing other encounter types in patients charts like telephone notes, patient gateway messaging, and other visits. This data collection will come from Epic chart review only. We will review the chart and summarize the nature of that conversation that was had around initiating SGLT-2is or GLP-1s, if one was documented. We will review the notes from the visit that was targeted by the intervention as well as subsequent notes in the chart as needed (such as telephone encounters, patient gateway encounters, and specialists visits notes) in order to understand if a medication was prescribed, and if not, then what the barriers were to starting. We will collect information on whether the patient filled the new prescription at the pharmacy, if available. This will include a total of 120 sampled charts, and the qualitative analyses will help us identify potential characteristics to extract from routine EHR data for Aim 2 and help understand remaining barriers to prescribing as well as potential mechanisms behind intervention effectiveness. Finally, we will also review the charts of all patients who received a prescription for a new medication to see what proportion of these prescriptions were actually filled by patients.

We will use the MGB standardized deployments of AI/ML services in MGB's secure cloud infrastructure, specifically the Azure OpenAI models as a tool to analyze qualitative data from the study and compare results from the LLM to those obtained by investigator analyses. Use of the LLM will permit faster analysis of large amounts of qualitative free-text data.

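### Deaths and SAEs are reported only as they come to the team's knowledge, with closer study contact in the intervention arms; a uniform EDW extraction in all arms would fix this

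*Combined protocol and SAP*

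**What the plan says.** Section 10.1 of the combined protocol and SAP counts an adverse event whether or not it is related to the research. Its SAE definition includes any death and any new or prolonged hospitalization.

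Reporting is then triggered by knowledge. "Any reports of deaths will be submitted to the NIA Program Officer" and the DSMB chair within 24 hours of the team learning of them, and unexpected SAEs follow within 48 hours. For the rest, "All other reported SAEs received by the study team will be reported to the NIA Program Officer and to the DSMB quarterly", unless the DSMB asks otherwise.

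The same section says that adverse events from prescribing are handled in regular care and "through established safety reporting and review systems within MGH". One study investigator "routinely reviews the safety reporting within MGH primary care and can be alerted to any reports that may relate to the study intervention". The investigators also "will be in direct contact with the peer PCPs to obtain ongoing feedback". Section 10.2 adds regular contact with clinical leadership.

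Under Section 6.2.1, the peer PCPs serve arms 1 and 2. In arm 2 the Central Authorization Unit also reviews charts and coverage and follows up individual cases. Arm 3 providers "will not receive any outreach outside of the end of study notification and survey". After the study, 20 prescribed and 20 non-prescribed charts per arm are sampled, and "we will also review the charts of all patients who received a prescription for a new medication" to see whether prescriptions were filled.

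The outcome extraction named in Section 6.2 covers prescribing and HbA1c. Deaths and hospitalizations are not mentioned.

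**The concern.** The definition is broad and the collection is passive. Under the definition, every death or hospitalization among about 1,468 patients with above-goal HbA1c and cardiovascular disease, kidney disease, heart failure or obesity is reportable. Under the reporting rule, only those that someone brings to the team are reported. The study has more contact with intervention providers than with usual-care providers, so the chance of an event being heard of may differ by arm even when the true risk does not.

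The primary outcome is unaffected. At stake is whether the DSMB, which Section 10.2 charges with monitoring participant safety, and the final report receive counts that are reasonably complete, have a known denominator and can be read across arms. Section 7 itself names hypoglycemia and allergic reactions as possible consequences of changed prescribing, and Section 10.1 states that "we expect any adverse events related to diabetes medication prescribing, such as hypoglycemia, to be the same as those experienced in routine clinical care". Passive receipt gives little basis for checking that expectation.

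**Working it through.** The plan gives no safety rate, expected event count or ascertainment figure, so there is nothing to reproduce. The check sets the routes side by side and then illustrates what unequal contact could do.

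**Step 1. Routes by which an event could reach the team**

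| Route | Section | Arms | Limit |
|---|---|---|---|
| MGH safety reporting | 10.1 | All | Alerts described only for reports that may relate to the intervention |
| Clinical leadership contact | 10.2 | Not stated to be arm-specific | General feedback |
| Peer PCP feedback | 10.1, 6.2.1 | 1 and 2 | Not described as event reporting |
| Authorization unit | 6.2.1 | 2 | Not described as event reporting |
| Sampled chart review, 20 + 20 per arm | 6.2.1 | All, equally | After study completion; purpose is conversations and barriers |
| Review of all prescribed patients | 6.2.1 | All, but size follows the primary outcome | Purpose is prescription fills |

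Two routes are not tied to arm on their face. The alert wording could tilt the first, because an event under usual care is less likely to look related to an intervention that the provider never received. No route is a systematic collection of deaths or hospitalizations.

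**Step 2. Charts opened after the study**

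Inputs from Sections 5.2, 6.2.1 and 9.2: 1,468 patients, 1:1:1 allocation of providers, control prescribing 30%, planned difference 11 points (so 41%), and 20 non-prescribed charts per arm. Assumptions: equal arms, the new medication is an SGLT-2i or GLP-1RA, and the 20 sampled prescribed charts fall within the review of all prescribed patients.

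- Patients per arm: 1468/3 = 489.3
- Control: 0.30 × 489.3 + 20 = 146.8 + 20 = 166.8, or 34.1%
- Each intervention arm: 0.41 × 489.3 + 20 = 200.6 + 20 = 220.6, or 45.1%
- Ratio: 220.6/166.8 = 1.32
- Non-prescribed charts opened: 20/342.5 = 6% in control and 20/288.7 = 7% in each intervention arm

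**Step 3. Ratio of events captured, intervention to control, with equal true risk**

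Let *b* be the share of events caught by arm-neutral routes, *q* the share caught through study contact in an intervention arm, and *f* the share of charts opened. Neither *b* nor *q* is in the documents; both are assumptions varied over a range. The routes are taken as independent and every event in an opened chart as noticed, which is generous to the chart review.

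- During the study: control = b; intervention = 1 − (1 − b)(1 − q)
- With chart review: control = 1 − (1 − b)(1 − 0.341); intervention = 1 − (1 − b)(1 − q)(1 − 0.451)

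| b | q | During study | With chart review |
|---|---|---|---|
| 0 | 0 | undefined | 1.32 |
| 0 | 0.3 | no control events captured | 1.81 |
| 0.25 | 0 | 1.00 | 1.16 |
| 0.25 | 0.1 | 1.30 | 1.24 |
| 0.25 | 0.3 | 1.90 | 1.41 |
| 0.5 | 0 | 1.00 | 1.08 |
| 0.5 | 0.1 | 1.10 | 1.12 |
| 0.5 | 0.3 | 1.30 | 1.20 |
| 1 | any | 1.00 | 1.00 |

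Example, b = 0.25 and q = 0.3 during the study: 1 − 0.75 × 0.70 = 0.475, and 0.475/0.25 = 1.90. The ratio is 1.00 whenever neutral capture is complete, which is what a uniform extraction aims at.

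**The case against.** The best case for the plan is that it has routes covering every arm. MGH safety reporting is institution-wide, a study investigator reviews it routinely, and leadership contact is not confined to the intervention arms. The chart reviews concern documented conversations, barriers and fills. Nothing says that SAEs will be abstracted from them, the sampled review is equal across arms, and it comes after study completion, so it could not shape what the DSMB sees during the six-month intervention. The available text promises case reports on knowledge, not counts by arm. The statement about routine care is a minimal-risk rationale, not a hypothesis to be tested between arms. Active collection in a trial of messages to providers may also be out of proportion, given the waiver of consent and HIPAA authorization (Section 5.1) and the commitment in Section 7 to use the minimum necessary data.

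Much of this stands. A reader might infer that events reach the team solely through arm-linked routes and that any by-arm list is therefore biased. The documents do not support that: arm-neutral routes exist, and no by-arm list is described. The DSMB's report format cannot be judged from the available text. A reader might also turn the 1.32 ratio of charts opened into an expected excess of SAEs. That would require full detection in every opened chart and no capture elsewhere. Nor is the EDW confined to prescribing and HbA1c; Sections 3 and 4.2 use it to identify eligible patients.

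The objection does not remove the gap between a definition that ignores relatedness and a collection that depends on who speaks to the team, nor the unequal contact by arm.

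**Conclusion.** The point holds as a gap in ascertainment, not as demonstrated bias. Deaths and SAEs will probably be under-counted, because no arm-independent collection is described. If the received events are viewed by arm, they are at risk of differential ascertainment, more likely toward higher counts in arms 1 and 2. The documents do not allow the size to be estimated: over the assumed values the capture ratio runs from 1.00 to 1.90, depending on two quantities the plan does not give. The 34% against 45% of charts opened rests on the planning rates and equal arms, and bears on safety only if reviewers pass on what they see. Neither the prescribing outcome nor its analysis is affected. This is a cheap improvement.

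**What to change.** Add to Section 10.1 a uniform EDW extraction of deaths and hospitalizations for all eligible patients in all three arms, whether or not prescribed, with the same eligibility rule and one fixed window with start and closing dates set in advance. Coded hypoglycemia and new allergy entries for either class are optional additions. Tabulate the results by the provider's randomized arm, over all eligible patients, for the DSMB and the final report. List events learned passively (from peers, the authorization unit, hospital reporting or chart review) separately, and state that these will not be compared by arm.

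The cost is modest because the source is already queried for these patients and the records can be extracted retrospectively. There are four downsides:

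- some analyst time;
- background events in the report that are unrelated to the intervention;
- a modest widening of data use under the HIPAA waiver, to be squared with the minimum-necessary commitment in Section 7;
- a need to state how extracted events fit the 24-hour, 48-hour and quarterly reporting in Section 10.1, since a batch extraction would otherwise start several clocks at once.

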10.2 Planned Safety Monitoring

General oversight of this project by the Brigham and Women's Hospital (BWH) pilot PI ([name]) will occur throughout the study period, including regular contact with MGB clinical leadership involved in the project to obtain ongoing feedback. In addition, this protocol will undergo Institutional Review Board (IRB) evaluation.

We will have oversight from both the NIA Director-approved Roybal Centers Program Data Safety Monitoring Board (DSMB) for all aspects of this research (see **Appendix A**). The DSMB will act in an advisory capacity to the NIA to monitor participant safety, evaluate the progress of the study, and review procedures and management of the study. Our plan for data and safety monitoring also includes oversight by the project principal investigators ([name]) throughout the study period.

Meetings of the DSMB will be held regularly (e.g., every six to nine months) at the call of NIA or the DSMB Chair and review data related to study protocols and ensure protection of patient confidentiality and safety. At each meeting, the DSMB will make recommendations as to whether the studies should continue or if changes to the protocol are necessary for continuation. This trial will also be registered with clinicaltrials.gov.

10.3 Data Management

To protect against the risk of inappropriate disclosure of personal health information, the investigators at MGH will only access study data with encrypted identifiers. As described, all members of the research team have completed or will complete appropriate human subjects research training and patient privacy training related to the Health Insurance Portability and Accountability Act (HIPAA). We have a history of collaborative evaluations with delivery organizations that involves transfer of the minimum data necessary to complete rigorous evaluations, involving the use of encrypted identifiers to ensure patient confidentiality.

To ensure the confidentiality and security of all data, the research team operates a secure, state-of-theart computing facility housed at MGB's data center. The MGB data center is a secure facility that houses both computing environments as well as clinical systems and electronic medical records for several large hospitals in Eastern Massachusetts. Entry into the computer room requires staffed computer room security. The Division's computers are connected to the MGB networking backbone with 10 gigabit-persecond fiber links. Network security is overseen by electronic medical records systems to the research team's data. All data are transmitted to programmers' workstations in an encrypted state. Backups are created using 256-bit AES encryption, the current Department of Defense standard for data security, and are stored in a locked facility. The redundancy, extensive data power, and security of our computer facility confirm our capacity to collect and manage data and ensure confidentiality for all project participants.

We will also safeguard any identifiable information from the physicians in accordance with IRB practices, limit access to any information in accordance with IRB practices, and limit access to the information to study investigators actively involved in the research who have all undergone human subjects research training.

For the use of the Azure Open AI models, we will utilize the secure MGB environment on the Azure cloud to access the Open AI tools. The cloud setup has been previously established by MGB for research team use and complies with the legal, cybersecurity, and data security requirements at MGB. Our team has completed a Cloud Architecture Consult with the MGB IT team and we will abide by MGB's published AI/LLM guidelines. Within the Azure environment, only team members included on the IRB who are participating in the data analysis will be given access to the LLM and data, following the same principles for our data management in other systems.

10.4 Outcomes monitoring

Given the minimal risks involved in participation in the study and its short duration, we will not perform any interim analysis for study outcomes.

10.5 Internal monitoring of source data, protocol adherence, and recordkeeping

The PI and study team will meet at least monthly to review study activity including recruitment, status of enrolled subjects, safety issues, internal quality assurance and peer review information. Meeting minutes will be maintained documenting the date of the meeting, names of those in attendance, and summary of information discussed and reviewed.

The Program Manager will complete an internal quality review of regulatory files prior to study enrollment begins and at least annually. The quality assurance review of regulatory files will be completed using the MGB Human Research Affairs Compliance and Education Office Regulatory Binder

Checklist. Any missing documents will be noted on the Regulatory Binder Checklist and then will be retrieved and filed as appropriate.

The Research Assistant(s) and Research Scientist will perform quality assurance reviews of the data entered into electronic case report forms for accuracy and completeness. Source data verification will be completed. Discrepancies will be documented for the study team to resolve. Once data entered on the eCRF have been verified and determined to be accurate and complete, the form will be locked the indicate that review is complete.

11 Privacy and Confidentiality

- Study procedures will be conducted in a private setting
- Only data and/or specimens necessary for the conduct of the study will be collected
- Data collected (paper and/or electronic) will be maintained in a secure location with appropriate protections such as password protection, encryption, physical security measures (locked files/areas)
- □ Specimens collected will be maintained in a secure location with appropriate protections (e.g. locked storage spaces, laboratory areas)
- Data and specimens will only be shared with individuals who are members of the IRB-approved research team or approved for sharing as described in this IRB protocol
- ☑ Data and/or specimens requiring transportation from one location or electronic space to another will be transported only in a secure manner (e.g. encrypted files, password protection, using chain-of-custody procedures, etc.)
- All electronic communication with participants will comply with Mass General Brigham secure communication policies
- ☑ Identifiers will be coded or removed as soon as feasible and access to files linking identifiers with coded data or specimens will be limited to the minimal necessary members of the research team required to conduct the research
- All staff are trained on and will follow the Mass General Brigham policies and procedures for maintaining appropriate confidentiality of research data and specimens
- ☑ The PI will ensure that all staff implement and follow any Research Information Service Office (RISO) requirements for this research
- Additional privacy and/or confidentiality protections

Data for the study will be safeguarded by state-of-the-art security protocols. The facilities have 24-hour security and are protected by locked entrances. MGB has computer networks in place that employ up to date virus protection software and enable password protected access only to study investigators. The setup for analysis of these data will be the same as all the other IRB applications that the MGB research division submits for secondary use of data. All the datasets, including limited protected health information (PHI), will be stored only on secure servers at MGB's data center and will only be accessed by a limited number of individuals in the study team from this division who are all trained in data security and patient privacy.

To ensure the confidentiality and security of all data, the research team operates a secure, state-of-theart computing facility housed at MGB's data center. The MGB data center is a secure facility that houses both computing environments as well as clinical systems and electronic medical records for several large hospitals in Eastern Massachusetts. Entry into the computer room requires staffed computer room security. The Division of Pharmacoepidemiology's computers are connected to the MGB networking backbone with 10 gigabit-per-second fiber links. Network security is overseen by electronic medical records systems to the research team's data. All data are transmitted to programmers' workstations in an encrypted state. Backups are created using 256-bit AES encryption, the current Department of Defense standard for data security, and are stored in a locked facility. The redundancy, extensive data power, and security of the computer facility confirm the capacity to collect and manage data and ensure confidentiality for all project participants.

